### **7.3 Vascular Permeability measurement**

$T_1$  weighted MR data will be collected before and after contrast agent administration. Permeability will be evaluated by applying dynamic contrast enhanced (DCE) scans for quantitative  $T_1$  measurements 4 times over 45 minutes and also 24±6 hours after contrast administration. Using the  $R_1$  ( $=1/T_1$ ) values,  $K^{trans}$  will can be calculated in the selected ROIs, (i. tumor core, ii. tumor rim, iii. ipsilateral control region iv. contralateral control region).

### **7.4 Ferumoxytol delayed MRI enhancement**

3 T and 7 T  $T_1$ -w scans acquired 24±6 hours post-ferumoxytol administration will be compared. Scans will be evaluated by two radiologists, measuring the enhancing volume from a volumetric  $T_1$ -w image set using a manual trace technique. Total delayed enhancement volumes will be calculated by multiplying the enhancing pixel area by the pixel volume. Volume measurements will be compared between 3T and 7 T.

### **7.5 Diffusion weighted imaging**

For diffusion evaluation, the same ROIs will be defined as were done for perfusion evaluation. (i. tumor core, ii. tumor rim, iii. ipsilateral control region iv. contralateral control region). Apparent diffusion coefficient (ADC) values will be calculated using Matlab environment (Mathworks, Natick, MA).

### **7.6 Time of flight angiography (TOF)**

Time of Flight angiography will be evaluated semi quantitatively by two radiologists. Vascular density will be compared between ferumoxytol and gadolinium and also between time points. We expect more visible vessels than without contrast agent. In our previous study TOF angiography was done after the injection of 4mg Fe/kg ferumoxytol. We hypothesize that the reduced dose of ferumoxytol also allows good visualization of blood vessels without leakage artifact.

### **7.7 Susceptibility weighted imaging:**

The size of the vascular structures within the tumor bed will be semi-quantitatively analyzed. The size of the tumor vessels will be compared to that of the normal penetrating vessels. Tumor vessels are considered to be small if their diameter is smaller than the diameter of the penetrating vessels. If the diameter is equal to or larger, they are determined to be medium and large respectively. The presence of tortuous vessels within the tumor bed is also recorded as present or absent. The resulting images will be evaluated in a blinded fashion by two neuroradiologists.

## **8 ETHICAL AND REGULATORY REQUIREMENTS**

### **8.1 Protocol Review**

The protocol and informed consent form for this study must be reviewed and approved in writing by the OHSU Knight Cancer Institute (CI) Clinical Research Review Committee (CRRC) and appropriate Institutional Review Board (IRB) prior to any subject being registered on this study.

## **8.2 Informed Consent**

Written informed consent will be obtained from all subjects, or the legally authorized representative of the subject, participating in this trial, as stated in the Informed Consent section of the case of Federal Regulations, Title 21, Part 50. If a subjects signature cannot be obtained, the investigator must ensure that the informed consent is signed by the subject's legally authorized representative. Documentation of the consent process and a copy of the signed consent shall be maintained in the subject's medical record.

## **8.3 Changes to Protocol**

Any modification of this protocol must be documented in the form of a protocol revision or amendment signed by the principal investigator and approved by the CRRC and IRB, before the revision or amendment may be implemented. The only circumstance in which the amendment may be initiated without regulatory approval is for a change necessary to eliminate an apparent and immediate hazard to the subject. In that event, the investigator must notify the CRRC and IRB in writing within 10 working days after the implementation. Investigators holding the IND must notify FDA of substantive changes to the protocol.

## **8.4 Maintenance of Records**

If the investigator relocates or, for any reason, withdraws from the study, the study records must be transferred to an agreed upon designee, such as another institution, another investigator, or to the OHSU Knight Cancer Institute Clinical Research Management. Records must be maintained according to sponsor or FDA requirements.

## **8.5 OHSU IRB Reporting of Unanticipated Problems and Adverse Events**

Unanticipated Problems (UP) and Adverse Events (AE) will be reported to IRB according to the policies, procedures and guidelines posted on the OHSU IRB web site

<http://www.ohsu.edu/research/rda/irb/policies.shtml>.

Fatal and life-threatening UP will be reported to OHSU IRB within 7 days of notification of the event. All other UP reports will be submitted to OHSU IRB no later than 15 days of occurrence or notification of the event. Copies of the report documents will be kept in the study regulatory binder.

UP and AE reports are submitted through OHSU e-IRB and will be reviewed by OHSU Knight Cancer Institute and IRB. Monthly accumulative reports will be reviewed by a DSMC Oncologist and forwarded to the CRRC.

## **8.6 MedWatch Reporting**

For this investigator-initiated study, the investigator is considered the sponsor. The investigator/sponsor is required to report adverse experiences to the FDA through the MedWatch reporting program, even if the trial involves a commercially available agent. Adverse experiences to be reported include any unexpected (not listed in the package label), serious adverse experiences with a suspected association to the study drug.

Adverse events that occur during clinical studies are to be reported to FDA as specified in the investigational new drug/biologic regulations using the FDA 3500A Mandatory Reporting form, which is available online at:

<http://www.fda.gov/Safety/MedWatch/HowToReport/ucm085568.htm>

This is available as a .pdf document for printing. (At this time, MedWatch does not have a 3500A form that can be submitted electronically).

When the serious adverse event is reported to the FDA, copies of the MedWatch 3500A form and supporting materials will be submitted to the OHSU Knight Cancer Institute and the IRB. A copy of the MedWatch 3500A form and supporting materials will be kept on file in the study regulatory binder.

## **8.7 OHSU Knight Cancer Institute Data and Safety Monitoring Plan**

In addition to complete study and pharmacy files, complete records must be maintained on each subject treated on this protocol. OHSU Knight Cancer Institute, through the auditing function of the Knight Clinical Trials Office, is responsible for ensuring that all member investigators and affiliate investigators conduct clinical research studies in compliance with local IRB standards, FDA regulations and NIH policies and in accordance with the Data and Safety Monitoring Plan policies and procedures <http://ozone.ohsu.edu/cancer/sharedres/kctoresdocs.cfm>

Locally initiated studies will be audited by OHSU Knight CI Auditor. Newly approved studies may be audited anytime after enrollment has been initiated. Each OHSU Knight approved treatment protocol will be audited on an annual basis in accordance with the Knight Data and Safety Monitoring Plan.

## **8.8 Inclusion of Women, Minorities and Children**

### **8.8.1 Inclusion of Women and Minorities**

No OHSU Knight Cancer Institute study will focus on any particular gender, racial or ethnic subset. No subject will be excluded from the study on the basis of gender, racial or ethnic origin. Male, female and minority volunteers will be recruited for this study from the general population and approximately 50% men and 50% women will be studied.

The projected gender, racial, and ethnic composition of the study will represent that of the state of Oregon.

**Table 5: Population Demographics - Oregon (%)**

Ethnic Category	Sex/Gender		
	Femal	Males	Total
Hispanic or Latino			11.7
Not Hispanic or Latino			88.3
Ethnic Category: Total of all subjects*			100*
Racial Category			
American Indian or Alaskan Native			1.4
Asian			3.7
Black or African American			1.8
Native Hawaiian or other Pacific Islander			0.3
White			83.6
More than one race			3.8
Unknown/Other			5.3
Racial Category: Total of all subjects*			100*
TOTALS	50.4	49.6	100*

**Source:** U.S. Census Bureau, 2010    \*Totals may not equal 100 due to rounding.

**Table 6: Projected Accrual for the Present Study (enter actual estimates, not percentages).**

Ethnic Category	Sex/Gender			
	Femal 9	Males 9	Unkn 0	Total 18
Hispanic or Latino	9	9	0	18
Not Hispanic or Latino	66	66	0	132
Unknown	0	0	0	0
Ethnic Category: Total of all subjects*	75	75	0	150*
Racial Category				
American Indian or Alaskan Native	1	1	0	2
Asian	3	3	0	6
Black or African American	2	1	0	3
Native Hawaiian or other Pacific Islander	0	0	0	0
White	62	63	0	125
More than one race	3	3	0	6
Unknown	4	4	0	8
Racial Category: Total of all subjects*	75	75	0	150*

Source: Investigator projections based on Table 5\*Totals must agree.

### 8.8.2 Inclusion of Children

This protocol does not include children for the following reason:

the number of children with this type of cancer is limited and limited dosing and adverse event data are currently available on the use of ferumoxytol in subjects <18 years of age, therefore, children are excluded from this study.

## **9 STATISTICAL CONSIDERATIONS**

### **9.1 Study Objectives**

Refer to section 1.

### **9.2 Baseline Summaries**

Descriptive statistics will be provided for all baseline characteristics including demographic variables (age, gender, race), disease characteristics (prior treatment, baseline KPS and steroid use), tumor characteristics (size and permeability) and pre-imaging variables. For continuous data, mean and standard deviation and minimum, median and maximum will be estimated. For categorical variables, the number and percent for each category will be estimated.

Data from those subjects already enrolled will be summarized both separately from the rest of the subjects and combined with the other subjects. These first eleven subjects will be considered as feasibility subjects. Summaries of imaging measures will include data on relative normalized signal intensity changes (CNR) for dynamic MRI data sets, cerebral blood volume and relative mean transit time for the perfusion data and  $K^{trans}$  for vascular permeability.

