#### **5.3.3 Day 1**

##### **Laboratory testing:**

- creatinine to calculate GFR prior to gadolinium administration (may be done up to 3 weeks prior)

- Urine pregnancy test in women of child bearing potential.

Imaging:

- Anatomical imaging on 3T & 7T and dynamic MRI (with gadolinium, see section 4.1) on either 3T or 7T (dependent on which group subject is assigned and as described in section 5.1.3)
- Day 1 and Day 2 imaging sessions may be separated by up to 7 days.
- A subset of 25 of the 150 subjects will only undergo MRIs on the 7T magnet.

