### **6 IMAGING SCHEMA AND ACQUISITION**

#### **6.1 Schema**

##### **Day 1**

1. Standard precontrast anatomical MRI sequences at 3T and/or 7T: sagittal T1, coronal FLAIR, MPRAGE, axial T1, T2, T2\*, PD weighted images and DWI.
2. TOF angiography
3. Quantitative T1 images
4. DSC MRI (T2\* weighted) for perfusion with Gd bolus administration dose: 0.1mmol/kg)
5. Quantitative T1 images for permeability measurement will be performed 4 times
6. TOF angiography (postgadolinium)
7. Standard postgadolinium imaging at 3T and 7T: MPRAGE, axial T1, T2, T2\* weighted images.

A subset of 25 of the 150 subjects will only undergo MRIs on the 7T magnet.

[Section 6.1 and 6.2 numbers 4 and 5 will be assigned to either 3 or 7 Tesla. 1, 2, 3, 6 and 7 will be performed on both magnet fields, the order of the scanners will be balanced, see Study Procedures section 5.2.3.] In subjects who cannot tolerate long MRI study either 3T or 7T (MRI with no dynamic imaging) pre-contrast sequences 1, 2 and 3 maybe acquired on Day 2 (dash line in the figure below).

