### **9.3 Descriptive Statistical Analyses**

All analyses described are viewed as descriptive in nature to better understand the variation in these parameters and not to provide definitive results as would be expected in a Phase III trial. The statistical analyses provide appropriate frameworks for assessing the relative magnitudes of effects while potentially controlling for other parameters of interest. Results will be used to plan for future definitive studies of the parameters that have appropriate power calculations and sample sizes. These analyses will be performed when target sample sizes are achieved and not on as interim analyses.

For Primary Aim 1, the primary descriptive comparisons are paired sample t-tests comparing the normalized signal intensity changes (CNR) for T1-weighted MRI signal at 3T and at 7T. Secondary analyses will use a repeated measures analysis of variance (ANOVA) model to compare 3T and 7T while adjusting for other factors including tumor type, prior therapy, and, potentially, important baseline factors that differ between the subjects assigned to the two field strengths. These tests are descriptive in nature and are not powered to provide a complete answer. Subjects who are scheduled to be imaged by a magnet of one field strength but are “crossed-over” to the other magnet or who otherwise fail to complete the scheduled imaging will not be included in these analyses. For the baseline characteristics, if two-sample tests of hypotheses indicate a significant difference ( $p<0.10$ ) between 3T and 7T signal intensity changes for a particular variable, that variable will be included in the ANOVA model as a covariate. Normality will be assessed graphically and, if needed, a transformation (e.g. the logarithmic transform) will be applied. These analyses will be performed for Gd T1-weighted MRI data only

For Primary Aim 2, the analyses will be similar to those for Aim 1 above using normalized (CNR) signal intensity decreases in the DSC data sets. . The same factors and analyses will be used. This objective assesses only Ferumoxytol.

For the first Secondary Aim, mixed model repeated measures ANOVA's will be fit. The outcomes will be relevant dynamic MRI (DCE and DSC) signal intensity changes for permeability and for perfusion. Factors will include imaging agent (Gd or ferumoxytol)

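### Sections 9.2 and 9.3 let post-contrast permeability enter the secondary 3T-versus-7T ANOVA as a baseline covariate, which can distort the field effect in either direction

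*Combined protocol and SAP*

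**What the plan says.** Section 9.2 places "tumor characteristics (size and permeability) and pre-imaging variables" in its list of baseline characteristics. Section 9.3 then screens the baseline characteristics. The trigger is a "significant difference ( $p<0.10$ ) between 3T and 7T signal intensity changes" for a given variable, and the consequence is "that variable will be included in the ANOVA model as a covariate".

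The model concerned is a secondary one: "Secondary analyses will use a repeated measures analysis of variance (ANOVA) model to compare 3T and 7T while adjusting for other factors". By contrast, "the primary descriptive comparisons are paired sample t-tests", which carry no covariates. Aim 2 (ferumoxytol DSC) is to be handled with the same factors and methods.

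On how permeability is obtained:

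- Section 7.3: "Permeability will be evaluated by applying dynamic contrast enhanced (DCE) scans for quantitative" T1, four times over 45 minutes and once more at 24±6 hours after contrast. K^trans is calculated from these values.
- Section 6.1, Day 1: "Quantitative T1 images for permeability measurement will be performed 4 times". This is item 5, after the gadolinium bolus in item 4, and both items are done on one magnet only.
- Section 5.3.3: "dynamic MRI (with gadolinium, see section 4.1) on either 3T or 7T", according to the subject's group. Section 5.3.4 keeps the Day 2 dynamic imaging on that same scanner.
- Section 1.1.1: comparing K^trans between 3T and 7T is the stated subject of Primary Aim 1.
- Section 3.1: eligibility asks only for standard MR imaging, so no permeability value is required before the study scans.

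**The concern.** A covariate in a comparison of two field strengths should be something the magnet cannot change. Permeability as defined in 7.3 does not meet that test. It is read by the scanner whose effect is being estimated, and Aim 1 treats it as something field strength may alter. The same quantity cannot safely be both a result of the exposure and a baseline adjuster for it.

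The fault lies in the type of variable admitted, not in the p<0.10 screen. Permeability would be just as unsuitable in a fixed covariate list. The screen adds to the problem, because a difference in measured permeability between the groups is what both triggers its inclusion and makes its inclusion harmful.

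At stake is the adjusted 3T-versus-7T effect. Section 9.3 says the results will be used to plan later definitive studies, so a distorted estimate could carry into their sample sizes.

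**Working it through.** The plan gives no effect size, SD or power, so there is no figure of its own to reproduce. The check has two parts.

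**Tracing the text.** Permeability is listed as baseline (9.2). Baseline characteristics are candidates for the ANOVA (9.3). The defined measure follows contrast and is tied to the assigned magnet for its dynamic series (7.3, 6.1, 5.3.3). Nothing in the documents removes it from the candidate list or defines a version that does not depend on field.

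**Size under assumptions.** Take one field per subject, as sections 5.3.4 and 6.1 provide for the dynamic series. Let F be field (0 = 3T, 1 = 7T) and P be true permeability (SD 1, same distribution in both groups).

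- Measured permeability: K = √0.8·P + √0.2·error + s·F, so its within-field SD is 1 and its reliability is 0.8.
- CNR = 0.50·F + r·P + noise, with within-field SD 1 and noise independent of the error in K.
- The within-field slope of CNR on K is r·√0.8, so the adjusted field effect = 0.50 − r·√0.8·s, with √0.8 = 0.894.

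The true effect (0.50 SD), the reliability, the correlation r and the shift s are all assumptions.

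| s (SD) | r | Calculation | Adjusted effect (SD) |
|---|---|---|---|
| 0.5 | 0 | 0.50 − 0 | 0.50 |
| 0.5 | 0.1 | 0.50 − 0.1×0.894×0.5 | 0.46 |
| 0.5 | 0.3 | 0.50 − 0.3×0.894×0.5 | 0.37 |
| 0.5 | 0.5 | 0.50 − 0.5×0.894×0.5 | 0.28 |
| 0.5 | 0.7 | 0.50 − 0.7×0.894×0.5 | 0.19 |
| 0 | any | 0.50 − 0 | 0.50 |
| −0.5 | 0.5 | 0.50 + 0.5×0.894×0.5 | 0.72 |

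**How often the screen would admit it.** Read the screen as a two-sample comparison of the variable between fields. For the numbers, take 150 subjects (5.1) less the 25 scanned only at 7T, then allow for 20% crossed over (5.6): (150 − 25) × 0.8 = 100, or 50 per field if split equally. The standardised difference is s/√(2/50) = 5s, to be set against 1.645. Selection is about 10% at s = 0, 35% at s = 0.25, 80% at s = 0.5 and nearly 100% at s = 1.0. The group size affects these rates but not the bias formula.

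**Cross-check.** A simulation of 6,000 trials per setting used slope 0.7 and measurement error SD 0.5 (reliability 1/1.25 = 0.8), with the shift in units of true-permeability SD.

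- At a shift of 0.5 the mean adjusted effect was 0.22, agreeing with 0.50 − (0.7/1.25)×0.5 = 0.22. The unadjusted effect was 0.50, the screen admitted permeability in 72% of trials, and the screened procedure averaged 0.26.
- At a shift of −0.5 the adjusted effect was 0.78.
- With no shift it stayed at 0.50 and adjustment gained precision (SD 0.16 against 0.20).
- If the errors in K and CNR correlate at 0.5, the value at a shift of 0.5 falls from 0.22 to 0.15.

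**The case against.** Several points on the other side have force.

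- **Only a secondary analysis is touched.** The paired t-tests come first and are unadjusted, and 9.3 calls all the analyses descriptive. This stands and limits the point.
- **Leakage may matter little for Aim 2.** Section 2.3 expects minimal USPIO leakage during the first pass, so the correlation between permeability and ferumoxytol DSC CNR may be low. This stands: the r = 0.5 and 0.7 rows suit an outcome driven by leakage better.
- **No mean shift is predicted.** A reader might infer that adjustment removes part of the field effect. The documents do not support a direction: the Aim 1 hypothesis is about the precision of K^trans maps, and an opposite shift inflates the effect.
- **The baseline item may not be K^trans.** Section 9.2 names K^trans separately among imaging measures, so baseline permeability could be some other descriptor. None is defined, however. A reader might also infer that every permeability value comes from the assigned magnet, but Day 3 quantitative T1 is acquired on both. Those scans still follow contrast and are not baseline.
- **The design may be paired.** Section 9.3 speaks of paired tests and of four agent-by-field measures per subject, whereas 5.3.4 and 6.1 put dynamic imaging on one magnet. In complete pairs, a single permeability value per subject cancels as a main effect. The distortion worked out here therefore applies if the one-magnet text governs.
- **The screening sentence is unclear.** Taken literally, it tests signal intensity changes rather than the baseline variable. Permeability is a candidate either way, but the selection rates hold only for the between-field reading.
- **Section 1.1 wants the impact of tumor permeability evaluated.** That can be done within each field strength without adjusting the field contrast for it.

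**Conclusion.** The point holds for the secondary ANOVA of Aims 1 and 2. As written, the plan can admit a covariate that is measured after contrast, largely by the magnet under comparison, and that Aim 1 treats as a result of field strength. Bias needs both a shift of measured permeability by field and a relation between permeability and CNR. If either is absent there is none.

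Its size is unknown because the documents give neither quantity. For a true effect of 0.50 SD, a 0.5 SD shift and reliability 0.8, the adjusted effect runs from about 0.46 (correlation 0.1) to 0.19 (correlation 0.7), and it exceeds 0.50 if the shift is reversed. For first-pass ferumoxytol the smaller distortions are plausible. The documents do not support a claim that the primary comparisons are compromised, or that the field effect must be understated. It is worth correcting because the correction costs almost nothing.

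**What to change.** In 9.3 add: *Permeability measured from study contrast imaging is not a candidate covariate in the 3T-versus-7T comparisons of Aims 1 and 2; its relation to the imaging measures is described within each field strength.* In 9.2, move permeability from the baseline characteristics to the imaging measures, summarised by field.

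If leakiness is to be explored in the field comparison, use permeability standardised within the field at which it was measured, as a labelled sensitivity analysis only. A surrogate from the Day 1 3T post-gadolinium images is not a way out, because the 25 subjects scanned only at 7T would not have it.

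The cost is one added sentence and one moved item, with no new data or scans.

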### **9.3 Descriptive Statistical Analyses**

All analyses described are viewed as descriptive in nature to better understand the variation in these parameters and not to provide definitive results as would be expected in a Phase III trial. The statistical analyses provide appropriate frameworks for assessing the relative magnitudes of effects while potentially controlling for other parameters of interest. Results will be used to plan for future definitive studies of the parameters that have appropriate power calculations and sample sizes. These analyses will be performed when target sample sizes are achieved and not on as interim analyses.

For Primary Aim 1, the primary descriptive comparisons are paired sample t-tests comparing the normalized signal intensity changes (CNR) for T1-weighted MRI signal at 3T and at 7T. Secondary analyses will use a repeated measures analysis of variance (ANOVA) model to compare 3T and 7T while adjusting for other factors including tumor type, prior therapy, and, potentially, important baseline factors that differ between the subjects assigned to the two field strengths. These tests are descriptive in nature and are not powered to provide a complete answer. Subjects who are scheduled to be imaged by a magnet of one field strength but are “crossed-over” to the other magnet or who otherwise fail to complete the scheduled imaging will not be included in these analyses. For the baseline characteristics, if two-sample tests of hypotheses indicate a significant difference ( $p<0.10$ ) between 3T and 7T signal intensity changes for a particular variable, that variable will be included in the ANOVA model as a covariate. Normality will be assessed graphically and, if needed, a transformation (e.g. the logarithmic transform) will be applied. These analyses will be performed for Gd T1-weighted MRI data only

For Primary Aim 2, the analyses will be similar to those for Aim 1 above using normalized (CNR) signal intensity decreases in the DSC data sets. . The same factors and analyses will be used. This objective assesses only Ferumoxytol.

For the first Secondary Aim, mixed model repeated measures ANOVA's will be fit. The outcomes will be relevant dynamic MRI (DCE and DSC) signal intensity changes for permeability and for perfusion. Factors will include imaging agent (Gd or ferumoxytol)

and field strength (3T and 7T). Each subject will contribute one measure for each combination of imaging agent and field strength (4 measures total). This will not be a definitive analysis as the power cannot be determined *a priori*. The mixed model allows for estimation of the means and confidence intervals for imaging agent and field strength (57). These data will be used to plan future comparative studies. For the second Secondary Aim, blood volumes will be compared using repeated measures ANOVA to compare the imaging agents. For the third Secondary Aim, analyses will add covariates of prior therapy to the analyses listed above. For the comparisons between treated and untreated subjects, means and confidence intervals will be estimated for each group for the perfusion and permeability measures and for the baseline characteristics listed above. Since prior treatment is likely confounded with other variables (e.g. disease severity), these comparisons will also be descriptive in nature and mainly be used to plan future studies.

For Secondary Aim five, the pathology will be analyzed qualitatively for the presence of iron staining. The amount and localization of the staining will be assessed, with attention paid to whether the tumor cells themselves or reactive cells in and around the tumor demonstrate iron uptake.

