### **5.2 Subject Registration**

- 5.2.1 Informed consent will be obtained, refer to section 8.2.
- 5.2.2 New subject registrations will be submitted to the study coordinator, who will record study data on all patients entered into the study and complete subsequent forms.
- 5.2.3 A subject's tumor type (primary versus metastatic) and prior treatment status (yes or no) determine to which of four strata the subject will be assigned. Subjects will be assigned to either 3T or 7T groups in an effort to keep the subgroups balanced and/or possibly depending on MRI availability. We expect up to 20% of subjects will not be able to complete the imaging at the assigned magnet strength and, further, that the proportion may be somewhat higher in those assigned to the 7T magnet (as this magnet is more likely to not be available due to technical and, more rarely, subjects may not be able to tolerate the more confined space). This approach is designed to, as well as possible, maintain balance between the 3T and 7T subgroups .

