#### **5.6 Subject Evaluability**

Subjects who are assigned to either the 3T or the 7T magnet strength MRI instruments may not be able to complete the imaging on the assigned strength on a given day. This will most likely be due to an MRI technical issue on the day the subject has been assigned. The 7T MRI is more likely to experience technical difficulties as this is a research instrument and is not a standard clinical product. In addition, a few subjects may not be able to tolerate an MRI examination on a particular day. If one MRI instrument is unavailable and the other one is available, the subject will be "crossed-over" for that day. For Primary Aims 1 and 2, crossing a subject on either day 1 or day 2 (but not both) will mean that the subject will be evaluable for one aim (corresponding to the non-crossover day) but not for the other. The sample size is adequate to allow up to 20% of subjects to be crossed over on at least one day. If one MRI instrument is not available on Study Day 3, data will be collected from that subject on only one instrument and these data will be used only to describe the range of values for that magnet strength.

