### 6.2.1 Option A

Three times in MRI on Day 1 (3T-7T-3T or 7T-3T-7T)	150
One time on MRI scanner Day 2 (3T or 7T)	90
Two times on MRI scanner Day 3 (3T and 7T)	100

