#### **9.5 Schema to maintain balance between 3T and & 7T groups**

Subjects will be assigned to a subgroup (with or without prior treatment) and will be assigned to undergo dynamic MR imaging at either 3T or 7T in an attempt to balance the subgroup. We expect up to 20% of subjects will not be able to complete the imaging at the assigned magnet strength and, further, that the proportion may be somewhat higher in those assigned to the 7T magnet (as this magnet is more likely to not be available due to technical and, more rarely, subjects may not be able to tolerate the more confined space. This approach is designed to, as well as possible, maintain balance between the 3T and 7T groups with respect to tumor type and prior treatment. This schema is not intended to provide the same validity as randomization within a Phase III trial as this is an exploratory study and not a definitive trial.

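### For outcomes measured at one field strength per subject, section 9.3 drops crossed-over subjects who were scanned that day, and sections 5.3.4 and 5.6 do not agree on what a Day 1 crossover costs

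*Combined protocol and SAP*

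**What the plan says.** **Assignment.** Under 5.2.3 subjects go to 3T or 7T to keep subgroups balanced "and/or possibly depending on MRI availability". Up to 20% are expected not to complete imaging at the assigned strength, and "the proportion may be somewhat higher in those assigned to the 7T magnet". Section 9.5 adds: "This schema is not intended to provide the same validity as randomization within a Phase III trial".

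**What is acquired where.** Section 6.1 states: "Section 6.1 and 6.2 numbers 4 and 5 will be assigned to either 3 or 7 Tesla". Those items are the DSC series and the repeated quantitative T1 series. The other items, including standard post-gadolinium T1, are done on both magnets. Option A in 6.2.1 has "One time on MRI scanner Day 2 (3T or 7T").

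**Crossover.** Section 5.6 says of failure to image at the assigned strength: "This will most likely be due to an MRI technical issue on the day the subject has been assigned". It continues "If one MRI instrument is unavailable and the other one is available, the subject will be" crossed over for that day. Crossing on one day only is said to cost the aim belonging to that day and to leave the other aim evaluable. Section 5.6 also calls the sample size adequate for up to 20% crossover, while 9.4 says the sample size has no statistical justification.

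**Day 2.** Section 5.3.4 puts the Day 2 dynamic imaging on whichever scanner was used for dynamic imaging on Day 1.

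**Analysis.** Section 9.3 makes paired t-tests of CNR the primary comparison for Aim 1 and uses the same analyses for Aim 2. A secondary model adjusts for tumor type, prior therapy and baseline differences between subjects assigned to the two strengths. Subjects who cross "to the other magnet or who otherwise fail to complete the scheduled imaging will not be included in these analyses".

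**The concern.** Field strength is the measurement condition under study. A DSC series acquired at 3T informs about 3T whichever magnet was scheduled. Excluding subjects because they left their assignment makes sense when assignment was randomised, and here it was not. The study's stated product is estimates for planning later trials, so the width of its confidence intervals is what the exclusion affects.

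A second problem concerns who is evaluable. A Day 1 crossover who then follows 5.3.4 has dynamic imaging on the unassigned magnet on both days and, under 9.3, is lost to both aims. Section 5.6 counts the same Day 1 event as the loss of one aim. Staff cannot follow both passages, and the Aim 2 analysis set depends on which is followed.

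**Working it through.** **The plan's own figure.** The adequacy statement in 5.6 cannot be reproduced, because no alpha, power, effect size or SD is given. What can be calculated is precision.

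**Inputs from the documents.** 150 subjects, of whom 25 are scanned only at 7T (5.1), leaving at most 150 − 25 = 125 for a 3T-versus-7T contrast. Crossover is up to 20% on at least one day (5.6).

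**Assumptions.** 1:1 assignment (62.5 per group), equal SD, one visit per subject, and a between-group comparison. If the 20% divides evenly over the two days, each aim loses 10%. To reflect more loss at 7T, that 10% is taken as 5% of the 3T group and 15% of the 7T group.

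**Formula.** 95% half-width in SD units = 1.96 × √(1/n3 + 1/n7).

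- No loss: 62.5 v 62.5 gives 0.351.
- Crossovers excluded: 62.5 × 0.95 = 59.375 and 62.5 × 0.85 = 53.125 give 0.370.
- Analysed as scanned: 59.375 + 9.375 = 68.75 and 53.125 + 3.125 = 56.25 give 0.352. The SE ratio is 0.370/0.352 = 1.05.
- Only half of those lost were scanned: 64.06 v 54.69 gives 0.361, a ratio of 1.026.
- All crossing from 7T to 3T (10% of 125 = 12.5 subjects): excluded 62.5 v 50 gives 0.372; as scanned 75 v 50 gives 0.358, a ratio of 1.04.
- Extreme case, the whole 20% on one aim's day and all scanned: with crossing split evenly between the magnets, √(1/0.8) = 1.118.

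**Evaluable subjects, 5.6 against 5.3.4.** With 125 subjects and 25 crossovers:

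- All on Day 1. Under 5.6, Aim 1 keeps 100 and Aim 2 keeps 125. Under 5.3.4 with 9.3, both keep 100.
- Half on Day 1. Under 5.6, each aim keeps 112.5. Under 5.3.4, the Day 1 crossovers carry forward to Day 2, and a Day 2 crossover to the other magnet cannot occur. If a Day 2 fault is met by rescheduling within the 7 days that 5.3.1 allows, Aim 2 loses only the Day 1 crossovers and keeps 112.5, the same as under 5.6. If Day 2 faults leave no scan, Aim 2 keeps 100.

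**Precision for Aim 2 if Day 2 faults leave no scan** (5%/15% on each day):

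- Excluded: 62.5 × 0.90 = 56.25 and 62.5 × 0.70 = 43.75 give 0.395.
- As scanned: 56.25 + 9.375 = 65.625 and 43.75 + 3.125 = 46.875 give 0.375, a ratio of 1.054.

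The recoverable gain is again about 5%, because only the Day 1 crossovers have a Day 2 scan to recover.

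**The case against.** **The paired test gains nothing.** A subject with dynamic data at one field strength adds no pair, whether crossed over or not. This stands. The half-widths above belong to a between-group analysis. The adjusted model in 9.3 points that way, since it allows for differences between the subjects assigned to each strength, but the paired test has to be resolved first.

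**Single-field acquisition is not beyond doubt.** Section 6.1 assigns DSC to one magnet, yet 9.3, for the first secondary aim, expects each subject to give four DCE/DSC measures, one per agent and field strength. For Aim 1, 9.2 ties CNR to the dynamic data sets, but post-gadolinium T1 images are taken on both magnets. If the CNR comes from those, the assigned magnet does not matter. The point is therefore conditional.

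**Section 5.3.4 is the default and 5.6 the exception.** This is a fair reading, since 5.3.4 mentions neither crossover nor aims. The loss of both aims is an inference from its same-scanner rule together with 9.3. Neither section says that it yields to the other, so a reconciling sentence is still needed.

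**The exclusion does protect something.** A reader might infer that it has no purpose. The documents do not support that: it is prespecified and keeps some of the tumor-type and treatment balance that 9.5 seeks.

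**The gain is small and the study descriptive.** Both are true. Visits may also be repeated up to four times, which the calculation ignores. These facts limit the size of the point; they do not give a reason to discard scans already made.

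**Conclusion.** The point holds in a limited form. For single-field outcomes analysed between groups, the exclusion widens the 95% interval by about 5% (0.370 against 0.352 SD), or 3–4% if only half were scanned or all crossing is from 7T to 3T. This rests on 125 comparative subjects, 1:1 assignment, equal SD and the assumed 5%/15% crossing. The ceiling, with all 20% on one aim's day, is about 12%.

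Sections 5.3.4 and 5.6 cannot both be followed after a Day 1 crossover. A reader might infer that following 5.3.4 doubles Aim 2's losses. The documents do not show this, because the same-scanner rule excludes separate Day 2 crossovers; the number lost depends on the day of crossover and on how Day 2 faults are handled. A reader might also infer bias from the higher loss expected at 7T. Selection is possible where a subject could not tolerate a scan, but 5.6 attributes most failures to technical faults, and bias is not shown.

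The adequacy statement in 5.6 has no support in 9.4.

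**What to change.** - State which images supply the Aim 1 CNR, and settle the paired t-test for outcomes acquired at one field strength per subject.
- For those outcomes, analyse by the field strength actually used that day, adjusted for tumor type and prior treatment. Keep the no-crossover set as a sensitivity analysis, and record the reason for each crossover.
- Reconcile 5.3.4 with 5.6, and say how a Day 2 scanner fault affects evaluability for each aim.
- Remove the adequacy sentence from 5.6, or replace it with the expected 95% half-width.
- Minor: say in section 9 whether the 25 subjects scanned only at 7T enter the 3T-versus-7T contrast, and whether the eleven feasibility subjects enter the 9.3 tests. Section 9.2 already has the eleven summarised both separately and combined.

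The cost is protocol and SAP wording. The downsides are less equal groups (about 69 v 56 in the example), more reliance on adjustment for the balance sought in 9.5, and some selection from tolerance-driven crossovers, which the sensitivity analysis would help to show.
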